2.2. Visit Windows

Nominal visits will be used for all by-visit analyses in the study unless otherwise specified, regardless of the scheduled visit window. The study visits scheduled should occur at the times delineated in the Time and Events Schedule of the protocol. All visits from Week 0 through Week 52 should occur within ± 7 days of the scheduled visit. If a study visit occurs outside this window, the sponsor should be consulted about how the subject should resume his/her normal dosing schedule relative to the baseline visit (Week 0). The other follow-up study visit should occur within ± 14 days of the scheduled visit.

2.3. Pooling Algorithm for Analysis Centers

Study centers will be pooled by region (NA, EU) as a stratification factor for the efficacy analyses if appropriate.

2.4. Analysis Sets

2.4.1. Efficacy Analysis Sets

2.4.1.1. Full Analysis Set

Full Analysis Set for Part 1

The efficacy analysis set for Part 1 of the study will be based upon the Full Analysis Set (FAS) which includes all randomized subjects in Part 1a and Part 1b. In the efficacy analyses, subjects will be analyzed according to their assigned treatment group regardless of their actual treatment received.

Depending on the endpoints, selected secondary efficacy analyses will be performed on subsets of all randomized subjects:

- PASI 90 responders withdrawn from study agent at Week 16
- PASI 90 responders withdrawn from study agent at Week 16 and later retreated with guselkumab
- PASI 90 non-responders at Week 16 who continued guselkumab treatment
- Etanercept subjects who crossed over to receive treatment of guselkumab

Full Analysis Set for Part 2

The efficacy analyses for Part 2 of the study will be based upon the Full Analysis Set which includes all subjects enrolled in Part 2.

Full Analysis Set for LTE

The efficacy analyses for Long Term Extension will be based upon the Full Analysis Set which includes all subjects who entered into the LTE period.

2.4.1.2. Per Protocol Analysis Set

The efficacy analysis for the co-primary endpoints will also be performed based on the per protocol analysis set. The per protocol population includes subjects in full analysis set except those

- who did not meet the inclusion criterion 2 in the protocol as listed below:
 - Have a diagnosis of chronic plaque-type psoriasis for at least 6 months (with or without PsA), prior to first administration of study intervention, defined as having at screening and baseline:
 - IGA ≥ 3 **and**
 - PASI ≥ 12 **and**
 - $\geq 10\%$ BSA involvement **and**
- at **least one** of the following:

-
- very thick lesions **or**
 - clinically relevant facial, genital, or hand/ foot involvement **or**
 - PASI \geq 20 **or**
 - >20% BSA involvement **or**
 - IGA=4
- who violated the exclusion diagnosis criteria 1 or 2:
 - Currently have nonplaque forms of psoriasis (eg, erythrodermic, guttate, or pustular).
 - Have current drug-induced psoriasis (eg, a new onset of psoriasis or an exacerbation of psoriasis from beta blockers, calcium channel blockers, or lithium).
 - who violated the concomitant or previous psoriasis medical therapies-related exclusion criteria (9, 11-19) as listed below:
 - Has previously received guselkumab or etanercept.
 - Has received any anti-TNF α biologic therapy (with the exception of etanercept, see exclusion 9) within the previous 3 months before the first administration of study intervention.
 - Has received any therapeutic agent directly targeted to IL-12/23, IL-17, or IL-23 within 6 months of the first administration of study intervention (including but not limited to ustekinumab, tildrakizumab, secukinumab, ixekizumab, risankizumab, or brodalumab).
 - Has received natalizumab, efalizumab, or agents that deplete B or T cells (eg, rituximab, alemtuzumab, abatacept, anakinra, or visilizumab) within 12 months of screening, or, if after receiving these agents, evidence is available at screening of persistent depletion of the targeted lymphocyte population.
 - Has received any systemic immunosuppressants (eg, methotrexate [MTX], azathioprine, cyclosporine, 6-thioguanine, mercaptopurine, mycophenolate mofetil, hydroxyurea, and tacrolimus) within 4 weeks of the first administration of study intervention.
 - Has received phototherapy or any systemic medications/treatments that could affect psoriasis or IGA evaluations (including, but not limited to, oral or injectable corticosteroids, retinoids, 1,25-dihydroxy vitamin D3 and analogues, psoralens, sulfasalazine, hydroxyurea, fumaric acid derivatives, herbal treatments, or traditional Taiwanese, Korean, or Chinese medicines) within 4 weeks of the first administration of study intervention.

- Has used topical medications/treatments that could affect psoriasis or IGA evaluations (including, but not limited to, corticosteroids, anthralin, calcipotriene, topical vitamin D derivatives, retinoids, tazarotene, methoxsalen, trimethylpsoralens, pimecrolimus, tacrolimus, or topical traditional Taiwanese, Korean, or Chinese medicines) within 2 weeks of the first administration of study intervention.
- Is currently receiving lithium, antimalarials, or intramuscular (IM) gold, or has received lithium, antimalarials, or IM gold within 4 weeks of the first administration of study intervention.
- Has received an experimental antibody or biologic therapy within the previous 6 months, or received any other experimental therapy or new investigational agent (topical or systemic) within 30 days or 5 half-lives (whichever is longer) of any study intervention administration or is currently enrolled in another study using an investigational agent or procedure.
- who did not complete the specified exposure to study agent as outline below
 - Subject randomized to guselkumab at Week 0 but did not receive all scheduled guselkumab administrations (ie, Week 0, Week 4, and Week 12), or received one or more extra guselkumab administrations.
 - Subject randomized to etanercept at Week 0 but missed two or more scheduled etanercept administrations (weekly dose through Week 15), or received one or more extra etanercept administrations.

Subjects who discontinued the study agent due to unsatisfactory therapeutic effect or an adverse event (AE) of worsening of psoriasis, or subjects who started prohibited medications and continued receiving study agents prior to Week 16 will be included in the per protocol analysis and the treatment failure rules specified in Section 5.1.3.3 will apply. Subjects who used rescue medication will also be included in the per protocol analysis and the rescue treatment rules specified in section 5.1.3.5 will apply.

Subjects who were excluded from the per protocol analyses will be summarized.

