### *Week 0 to Week 16 (Placebo-Controlled Period)*

The guselkumab and placebo administrations will be administered by site personnel at the study site. Etanercept will be administered at the study site at Week 0. Subsequent weekly doses of etanercept through Week 15 may be administered at the study site or be self-administered at home by the participant or caregiver on weeks without a site visit. The dose regimens are as follows:

- **Group I:** Weight-based guselkumab dose up to CCI SC at Weeks 0, 4, and 12.
- **Group II:** Weight-based placebo for guselkumab dose administered SC at Weeks 0, 4, and 12.
- **Group III:** Weight-based etanercept dose up to 50 mg SC weekly through Week 15.

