A participant will not be automatically withdrawn from the study if he or she must discontinue treatment before the end of the treatment regimen. Participants who discontinue study intervention but do not terminate study participation will continue to return for protocol-specified procedures and evaluations for at least 12 weeks following the last dose of study intervention. The procedures and evaluations listed for the Study Termination Visit, should also be performed 12 weeks after the last dose of study intervention.

All procedures and evaluations must be conducted prior to a participant's withdrawal of consent.

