At baseline in Part 1, approximately 40 participants (30 in Part 1a and 10 in Part 1b) will be randomized to guselkumab, and approximately 25 participants (15 in Part 1a and 10 in Part 1b) will be randomized to placebo.

As shown in [Table 1](#), with the conservative assumptions of response rates of 65% in the guselkumab treatment group and 13% in the placebo group, the proposed 40 participants in the guselkumab group and 25 in the placebo group provide at least 99% power to detect a significant difference in the proportion of IGA responders (0 or 1) and PASI 75 responders at Week 16 separately between the guselkumab and placebo treatment groups at a 2-sided significance level of 0.05. These sample sizes are also chosen to ensure sufficient power for major secondary endpoints.

Table 1: Power to Detect a Treatment Effect for Guselkumab Based on Different Assumptions of Response Rates

Endpoint		Power
IGA Score of 0 or 1/PASI 75 at Week 16		
Placebo (n=25)	Guselkumab (n=40)	
13%	65%	>99%
13%	70%	>99%
13%	75%	>99%
13%	85%	>99%

IGA=Investigator's Global Assessment; PASI=Psoriasis Area and Severity Index

Assumptions for Etanercept Response Rates

The PGA responder (0 or 1) rate in the etanercept group of the etanercept pediatric plaque psoriasis study was 53% and the PASI 75 rate was 57%. Therefore, a range of response rates from 53% to 60% for both IGA 0/1 and PASI 75 in the etanercept active comparator treatment group is utilized for the proposed pediatric study.

Power for Etanercept and Placebo Comparisons

With approximately 25 participants (15 in Part 1a and 10 in Part 1b) randomized to receive etanercept, and approximately 25 participants (15 in Part 1a and 10 in Part 1b) in the placebo group, there will be at least 81% power to detect a significant difference in the proportion of IGA responders (0 or 1) and PASI 75 responders at Week 16 separately between etanercept and placebo treatment groups at a 2-sided significance level of 0.05 ([Table 2](#)).

Table 2: Power to Detect a Treatment Effect for Etanercept Based on Different Assumptions of Response Rates

	Endpoint		Power
	IGA Score of 0 or 1/PASI 75 at Week 16		
Placebo (n=25)		Etanercept (n=25)	
13%		53%	81%
13%		55%	85%
13%		60%	92%

IGA=Investigator's Global Assessment; PASI=Psoriasis Area and Severity Index

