5.2.4. Data Handling

Subjects who meet treatment failure criteria specified in Section 5.1.3.2 or rescue treatment criteria in Section 5.1.3.4 prior to Week 16 will be considered not to have achieved an IGA score of cleared (0) or minimal (1) or a PASI 75 response at Week 16. In addition, subjects with a missing IGA or PASI score at Week 16 or who do not return for evaluation at Week 16 will be considered not to have achieved the respective endpoint at Week 16.

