5.2.7. Per Protocol Analyses

Per protocol analyses will be performed for the co-primary endpoints, similar to the primary analyses but based on the per protocol analysis set as defined in Section 2.4.1.2.

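### The per-protocol set excludes guselkumab and etanercept participants for missed or extra doses but has no such rule for placebo, so exclusion depends on arm

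*SAP*

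**What the plan says.** SAP 2.4.1.2 defines the per-protocol set as the full analysis set minus several groups. One group is participants who did not complete the specified exposure to study agent, and that exclusion is limited to the cases listed beneath it. There are two:

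- Guselkumab: "Subject randomized to guselkumab at Week 0 but did not receive all scheduled guselkumab administrations" at Weeks 0, 4 and 12, or any extra guselkumab administration.
- Etanercept: "Subject randomized to etanercept at Week 0 but missed two or more scheduled etanercept administrations", or any extra etanercept administration.

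There is no placebo case. Protocol section 6.1 gives the placebo regimen as "Weight-based placebo for guselkumab dose administered SC at Weeks 0, 4, and 12", the same visits as guselkumab.

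The same SAP section keeps in the set, in every arm, participants who stopped for lack of effect or worsening psoriasis, those who started prohibited medication while continuing study agent before Week 16, and those who used rescue. It also says: "Subjects who were excluded from the per protocol analyses will be summarized".

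SAP 5.2.7 describes the per-protocol analysis of the co-primary endpoints as "similar to the primary analyses but based on the per protocol analysis set", and adds no placebo rule. Protocol 9.4.1.3 leaves the per-protocol details to the SAP.

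**The concern.** Guselkumab and placebo are blinded to each other through Week 16, use identical devices and follow one schedule. A dosing rule that can be written for one can be written for the other. As the plan stands, post-randomization removal from the guselkumab-versus-placebo comparison depends on assigned arm. Two situations are handled unevenly.

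**Missed injection, reason unrelated to efficacy.** The guselkumab participant leaves the set. The placebo participant stays. If the placebo participant has no Week 16 score, SAP 5.2.4 makes them a non-responder, since that rule covers "subjects with a missing IGA or PASI score at Week 16 or who do not return for evaluation at Week 16". If they are still being seen at Week 16, the observed score counts. Protocol 7.1 allows for this: those who stop treatment but remain in the study "will continue to return for protocol-specified procedures and evaluations for at least 12 weeks following the last dose of study intervention".

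**Wrong treatment.** A guselkumab participant given placebo at a dosing visit is removed, because not all guselkumab doses were received. A placebo participant given guselkumab before Week 16 stays in the placebo arm.

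The first situation can flatter guselkumab and the second works against it. At stake is the value of the per-protocol result as a check on the co-primary finding. The finding itself is not at risk.

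**Working it through.** **Inputs from the documents.** SAP 1.4 plans 40 guselkumab and 25 placebo participants, and calculates power "with the conservative assumptions of response rates of 65% in the guselkumab treatment group and 13% in the placebo group" at a two-sided 0.05 level.

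**Plan's own figure.** Exact power of the two-sided Fisher test (unstratified, by binomial enumeration) for 65% of 40 versus 13% of 25 is 99.3%, which agrees with the stated figure of more than 99%. No figure in the plan is attached to the per-protocol set.

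**Assumptions.** The documents give no missed-dose rate. Let m be the share of each arm that breaks the dosing rule for reasons outside the retained categories, with m = 5%, 10%, 20%. Treat 65% and 13% as full-set rates, a difference of 52.0 points.

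**Case 1: everyone who misses a dose is a non-responder.**

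- As written (guselkumab only excluded): 0.65/(1−m) − 0.13
- Same rule in both arms: 0.65/(1−m) − 0.13/(1−m)
- Tilt from the asymmetry: 0.13·m/(1−m)

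| m | As written | Same rule in both arms | Tilt |
|---|---|---|---|
| 5% | 68.42 − 13.00 = 55.42 | 68.42 − 13.68 = 54.74 | 0.68 |
| 10% | 72.22 − 13.00 = 59.22 | 72.22 − 14.44 = 57.78 | 1.44 |
| 20% | 81.25 − 13.00 = 68.25 | 81.25 − 16.25 = 65.00 | 3.25 |

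Most of the movement away from 52.0 does not come from the asymmetry. At m = 10% the per-protocol difference is 59.2 − 52.0 = 7.2 points above the full-set value, and 57.8 − 52.0 = 5.8 of those would remain with a rule in both arms.

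**Case 2: placebo participants who miss doses respond at r times the rate of completers.** The completer rate is 0.13/(1−m+m·r), so the tilt is 0.13/(1−m+m·r) − 0.13.

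| r | m = 5% | m = 10% | m = 20% |
|---|---|---|---|
| 0 (Case 1) | 0.68 | 1.44 | 3.25 |
| 0.5 | 0.33 | 0.68 | 1.44 |
| 0.8 | 0.13 | 0.27 | 0.54 |
| 1 | 0 | 0 | 0 |

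**Whole numbers.** Suppose 26 of 40 on guselkumab and 3 of 25 on placebo respond, and four guselkumab and two placebo participants miss a dose, all non-responders.

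- As written: 26/36 − 3/25 = 72.2 − 12.0 = 60.2 points (unstratified Fisher p = 0.000005)
- Same rule in both arms: 26/36 − 3/23 = 72.2 − 13.0 = 59.2 points (p = 0.00001)

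**Opposite direction.** Suppose instead that no placebo participant misses a dose, but one is given guselkumab in error and responds, making 4 of 25.

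- As written: 26/36 − 4/25 = 72.2 − 16.0 = 56.2 points (p = 0.00002)
- With that participant removed: 26/36 − 3/24 = 72.2 − 12.5 = 59.7 points (p = 0.000005)

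**Cost in power of a rule in both arms.** With rates held at 65% and 13%, Fisher power is 98.9% for 38 versus 24, 98.0% for 36 versus 22, and 97.6% for 32 versus 20.

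**The case against.** The strongest reply is that the rule concerns exposure to active drug. Missing an inert injection changes no exposure and gives no pharmacological reason to respond less, so r should be near 1 for any placebo participant observed at Week 16. Efficacy-related discontinuations and rescue users stay in the set in every arm, and follow-up runs at least 12 weeks past the last dose, so someone last dosed at Week 4 is due to be seen through 4 + 12 = Week 16. Site staff give the injections at the site in this period, so 20% missed dosing looks high. This stands as far as size goes: the Case 1 figures are a ceiling. It does not remove the asymmetry. Someone last dosed at Week 0 has assured follow-up only to Week 12, and anyone without a Week 16 score becomes a non-responder on placebo but is removed on guselkumab.

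Second, the direction is not settled. One wrong-treatment responder moves the difference by 59.7 − 56.2 = 3.5 points against guselkumab, more than the largest tilt in its favour. This is correct, and it means the bias cannot be given a sign in advance.

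Third, SAP 4.3 tabulates randomized against actual treatment, and SAP 4.5 lists major deviations, including wrong treatment, by randomized arm. These make the cases visible but do not change who is in the per-protocol set.

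Fourth, the two active arms already have different missed-dose thresholds. They also have different dosing frequencies, which guselkumab and placebo do not. The term study agent could be read to include placebo, but the text confines the exclusion to the listed cases.

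**Conclusion.** The concern holds. Followed exactly, SAP 2.4.1.2 makes removal from the per-protocol guselkumab-versus-placebo comparison depend on arm, and nothing in either document supplies the missing placebo rule.

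It is a minor point. The tilt lies between zero and about 0.7, 1.4 or 3.3 points at assumed missed-dose rates of 5%, 10% and 20%. The upper values require every placebo participant who misses a dose to be a non-responder. It is small because it scales with the low placebo response rate. A wrong-treatment case can outweigh it in the other direction. Every example keeps a difference above 56 points and the same conclusion. The full-analysis-set primary test and both the global and the US-FDA testing sequences are untouched. The change is worth making because it is nearly free and gives the supportive analysis the same entry rule in both blinded arms.

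**What to change.** Add a third exposure bullet to SAP 2.4.1.2. A participant randomized to placebo is excluded if any of the Week 0, 4 or 12 placebo injections was missed, if any extra injection was given, or if guselkumab was received before Week 16. Lay out the already planned summary of per-protocol exclusions by arm and reason.

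The protocol's Appendix 2 says enrollment is closed, but neither document gives a Week 16 lock date. If that lock has passed, keep the set as defined and report the version with the placebo rule as a labelled sensitivity analysis.

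The cost is one SAP bullet, one line of derivation code and a table layout.

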## **6.5. Concomitant Therapy**

Concomitant therapies must be recorded throughout the study from screening and continuing until 12 weeks after the last dose of study intervention. Concomitant therapies should also be recorded beyond that point only in conjunction with SAEs that meet the criteria outlined in Serious Adverse Events in Section 8.3.1, Time Period and Frequency for Collecting Adverse Event and Serious Adverse Event Information.

All therapies (prescription or over-the-counter medications, including vaccines, vitamins, herbal supplements) different from the study intervention, as well as all shampoos used to treat plaque psoriasis, moisturizers, or emollients, must be recorded in the CRF. Modification of an effective preexisting therapy should not be made for the explicit purpose of entering a participant into the study.

If a prohibited therapy is administered during the active treatment phase including the LTE, unless agreed to by the medical monitor, the participant should be discontinued from study treatment. If a prohibited therapy is initiated during the safety follow-up period (12 weeks between last administration of study intervention and final site visit), the participant should still complete his or her final study visit, and the medication should be recorded as a concomitant medication.

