### **7.1. Discontinuation of Study Intervention**

A participant's study intervention must be discontinued if any of the following occur:

- The investigator believes that for safety reasons or tolerability reasons (eg, AE) it is in the best interest of the participant to discontinue study intervention
- An AE temporally associated with study intervention injection, resulting in bronchospasm with wheezing and/or dyspnea requiring ventilatory support, or symptomatic hypotension (defined as systolic BP <  $[70 + (2 \times \text{age in years})]$ ).
- The participant or their legally acceptable representative withdraws consent/assent for administration of study intervention.
- Pregnancy, or pregnancy planned within the study period or within 12 weeks after the last study intervention injection.
- The initiation of protocol-prohibited medications or treatments as outlined in Section 6.5, Concomitant Therapy, unless agreed to by the sponsor medical monitor.
- The participant is diagnosed with a malignancy.

- An opportunistic infection.
- A recurrent or chronic serious infection.
- A severe study intervention injection-site reaction.
- The participant meets one of the following TB criteria:
  - A diagnosis of active or latent TB is made.
  - A participant has symptoms suggestive of active TB based on follow-up assessment questions and/or physical examination or has had recent close contact with a person with active TB and cannot or will not continue to undergo additional evaluation.
  - A participant undergoing evaluation has chest imaging with evidence of TB and/or a positive IGRA test result and/or 2 indeterminate/borderline IGRA test results. Indeterminate/borderline or suspected false-positive tests should be handled as outlined in Section 8.
- The participant has liver test abnormalities as described in Section 8.2.3 and Appendix 12 (Section 10.2). Such abnormalities would include the following:
  - ALT or AST >8 x ULN
  - ALT or AST >5 x ULN for more than 2 weeks
  - ALT or AST >3 x ULN **and** (total bilirubin >2 x ULN or international normalized ratio [INR] >1.5)
  - ALT or AST >3 x ULN **and** symptoms of hepatitis (eg, fatigue, nausea, vomiting, right upper quadrant pain or tenderness, fever, rash, and/or eosinophilia [>5%])
- The participant is unable to adhere to the study visit schedule or comply with protocol requirements.

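### The per-protocol set drops guselkumab participants stopped for starting a prohibited psoriasis therapy before the Week 12 dose, although the SAP counts them as treatment failures

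*SAP*

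**What the plan says.** SAP 2.4.1.2 starts from inclusion: "The per protocol population includes subjects in full analysis set except those" who meet a listed exclusion. Most of the listed exclusions concern eligibility. The last concerns exposure. For guselkumab it reads "Subject randomized to guselkumab at Week 0 but did not receive all scheduled guselkumab administrations", the scheduled doses being Weeks 0, 4 and 12. For etanercept it reads "Subject randomized to etanercept at Week 0 but missed two or more scheduled etanercept administrations". No exposure exclusion is written for placebo.

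The section then keeps two groups of treatment failures, with the failure rules applied. The first is "Subjects who discontinued the study agent due to unsatisfactory therapeutic effect or an adverse event (AE) of worsening of psoriasis". The second is worded so that "subjects who started prohibited medications and continued receiving study agents prior to Week 16 will be included in the per protocol analysis". Users of rescue medication are also kept, with no condition on continued dosing.

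Protocol 7.1 lists among the reasons for which study intervention must be discontinued "The initiation of protocol-prohibited medications or treatments as outlined in Section 6.5, Concomitant Therapy, unless agreed to by the sponsor medical monitor". Protocol 6.5 says the same: "unless agreed to by the medical monitor, the participant should be discontinued from study treatment".

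SAP 5.1.3.2 counts starting a prohibited therapy that could affect psoriasis as treatment failure, with no reference to whether study drug continues. SAP 5.1.3.3 then assigns non-response to the binary endpoints from that point onward.

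**The concern.** SAP 5.1.3.2 treats three events alike: stopping for lack of efficacy, stopping for an adverse event of worsening psoriasis, and starting a prohibited therapy. The per-protocol definition does not. The first two are kept after study drug stops; the third is written back in only if study drug continued.

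That condition misses the participants who need the exception. Someone who started a prohibited therapy and still received all three guselkumab doses does not meet the exposure exclusion and needs no exception. Someone who was stopped and missed a dose does meet it and gets none. The participant managed by the protocol's default is removed, while one left on drug stays in as a failure.

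The excluded participant is a non-responder by rule, so the exclusion depends on the outcome. It enters a planned analysis of both co-primary endpoints (SAP 5.2.7) and can move the guselkumab rate in one direction only.

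**Working it through.** **1. Planning inputs.** SAP 1.4 gives 40 guselkumab and 25 placebo participants, 65% to 85% response on guselkumab and 13% on placebo, at two-sided 0.05. The plan states no figure for the per-protocol set, so its power figures serve only to check these inputs. Power was computed as the sum, over all pairs of binomial counts, of the probability of each pair for which the unstratified two-sided Fisher p is at most 0.05 in favour of active treatment.

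- Guselkumab at 65%, 70%, 75% and 85%: 99.3%, 99.8%, above 99.9% and above 99.9%. The plan states above 99% for each.
- Etanercept (25 versus 25) at 53%, 55% and 60%: 81.0%, 84.9% and 92.4%. The plan states 81%, 85% and 92%.

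The stated figures reproduce.

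**2. Who is kept.** Take a guselkumab participant who starts a prohibited psoriasis therapy before Week 16 and meets no eligibility exclusion. All rows are non-responders under SAP 5.1.3.3.

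| What happens next | Misses a Week 4 or 12 dose? | Covered by an exception? | In the per-protocol set? |
|---|---|---|---|
| Left on drug with the medical monitor's agreement, all doses received | No | Not needed | Yes |
| Stopped after the Week 12 dose | No | Not needed | Yes |
| Stopped before the Week 12 dose, reason recorded as lack of efficacy or worsening psoriasis | Yes | Yes, the first | Yes |
| Stopped before the Week 12 dose, reason recorded as prohibited therapy | Yes | Neither | **No** |

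Only the last row is lost. An etanercept participant stopped on the same ground with two or more weekly doses outstanding falls into the same gap. A placebo participant does not, because no exposure exclusion is written for that arm.

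**3. Effect on the guselkumab rate.** With R responders among N, dropping k non-responders changes the rate from R/N to R/(N − k), a rise of Rk/[N(N − k)]. Other per-protocol exclusions are ignored. The documents do not give k.

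| k | R = 26 (65%) | R = 34 (85%) |
|---|---|---|
| 0 | 26/40 = 65.0% | 34/40 = 85.0% |
| 1 | 26/39 = 66.7% (+1.7 points) | 34/39 = 87.2% (+2.2) |
| 2 | 26/38 = 68.4% (+3.4) | 34/38 = 89.5% (+4.5) |
| 4 | 26/36 = 72.2% (+7.2) | 34/36 = 94.4% (+9.4) |

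**4. Effect on the comparison.** Take placebo at 3/25 = 12.0%, the nearest whole count to 0.13 × 25 = 3.25. With R = 26 the difference is 53.0 points at k = 0, 54.7 at k = 1 and 56.4 at k = 2. The unstratified Fisher p is 2.9 × 10⁻⁵ at k = 0 and 4.7 × 10⁻⁶ at k = 4. Significance does not change.

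**The case against.** The path is narrow. The therapy must start early enough to cost the Week 4 or Week 12 dose, the medical monitor must not agree to continuation, the product must not be eligible rescue steroid, and the stop must not be recorded as lack of efficacy or worsening psoriasis. The therapies that count as failures are mainly those used for psoriasis, so many such stops could be recorded as lack of efficacy and would then be kept. The per-protocol analysis lies outside the testing sequence. SAP 2.4.1.2 promises a summary of those excluded, and SAP 4.2 a listing of treatment failures with reasons, so any case would be visible. All of this stands. It limits how often the gap matters, but does not close it, and it shows that membership can turn on how the reason for a stop is coded.

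The size of the shift in the treatment difference is also not due to this clause alone. It equals the shift in the guselkumab rate only because placebo has no exposure exclusion. With such a rule, placebo failures could be lost as well and the net shift could be smaller.

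A reader might infer that every prohibited-therapy starter who is taken off drug is dropped. The text does not support that: inclusion is the default, and someone stopped after the Week 12 dose has had every scheduled dose. A reader might also infer that this clause alone decides whether the per-protocol result is unbiased. It does not. The exposure criterion also conditions on doses missed for other reasons after randomisation, and would still do so once the clause is changed.

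**Conclusion.** The gap is real and minor. A known treatment failure leaves the guselkumab per-protocol set when the stop is attributed to prohibited therapy and costs the Week 4 or Week 12 dose; nothing else in the SAP brings that participant back. The etanercept rule has the same gap.

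If one or two of 40 are affected, the per-protocol guselkumab rate rises by 1.7 or 3.4 points at a 65% response, and by 2.2 or 4.5 points at 85%. This rests on the planned arm size, on whole-number responder counts, and on an assumed number of cases. The direction is certain if any case occurs.

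It would go too far to say that the response rate is inflated as a matter of fact, since zero cases give zero shift. Nor is the primary conclusion at risk: SAP 5.2.3 and 5.2.4 analyse all randomised participants and count these failures as non-responders.

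**What to change.** In SAP 2.4.1.2, delete the condition that prohibited-therapy starters continued study agent. Add that participants who meet any treatment-failure criterion of 5.1.3.2 before Week 16 are not removed by the exposure criterion, in either active arm, and are analysed as non-responders under 5.1.3.3. State that the eligibility-based per-protocol exclusions (inclusion criterion 2 and the listed exclusion criteria) still apply; otherwise the new sentence could be read as overriding them.

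The same edit would be needed if a placebo exposure rule were added later, because that rule would otherwise delete placebo failures in the same way.

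The cost is one clause of SAP text and one line of analysis-set programming. The per-protocol guselkumab rate may become slightly less favourable. The change concerns the analysis set only and leaves the protocol's stopping rule as it is.
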